4.4 Sample size

We will include 150 people with neuropathic ulcers due to leprosy and diabetes in the study (75 each from India and Nepal). If adherence is 0.5 (50%) then the 95% CIs (n=150) would be 0.42 to 0.58. Any other proportion would provide narrower CIs. We do not anticipate observing a difference in ulcer healing between intervention and control because, given a control healing rate of 70%, the intervention group would have to be 90% to have a 80% power.

4.4.1 Inclusion criteria

Patients aged 18 years and above with loss of sensation (inability to feel monofilament of 10 grams) and plantar ulcer in the foot due to leprosy or diabetes. Patients with multiple or bilateral ulcers will be included alongside those with just one ulcer.

4.4.2 Exclusion criteria

Patients with:

- multiple plantar ulcers where largest ulcers cannot be offloaded effectively due to presence of other ulcers
- sign of infection or infected ulcer or with the signs of sinus tracks
- insensitive feet along with orthopaedic conditions in the ankle, knee and hip or limb length discrepancy
- amputation; forefoot and above on the contralateral leg.
- patients who are wheelchair dependent

4.5 Intervention and control group

Intervention group: Removable walker boot with a customised insole will be applied to off-load the ulcer area(s). This removable nature facilitates daily dressing of the ulcer and monitoring its progress. This also allows patient mobility to carry out essential activities of daily living. The details of the intervention are described below.

Control group: The current standard of care provided in the community; the Micro-cellular rubber footwear.

Other than the difference in the off-loading methods, the dressings and self-care education provided will be the same between the groups. The dressings will be done by patient themselves or by caregivers who will be provided with required materials and training for dressing. Study participants will receive information on the importance of off-loading to aid ulcer healing, with an emphasis on the need for adherence to the off-loading methods. On completion of the trial, patients in the intervention and control group will be provided with appropriate MCR footwear to prevent recurrence of ulcer.

4.5.1 Description of intervention and control intervention

The Intervention – Removable walker boot: The removable walker is a brace which offers stabilization and immobilization to the foot, ankle and lower leg with comfort which can help in off-loading the ulcer area through pre-cut insole (more details on making of insole is given below). The removable walker boot (Figure 1) works on exactly the same principle as total contact cast(11) in off-loading the ulcer area except that it is removable. The material that covers the leg is soft and facilitates proper fitting with the removable property allows wound inspection, dressing and hygiene. It has a sufficient broad bottom sole promotes natural gait, reduces plantar pressure and at the same time provides stability. The rigid stirrup in both sides provides stability and immobilization to the ankle joint while walking.

1c: Cut-out soft insole to off-load

Figure 1: Illustration of removable walker boot with cut out soft insole to offload ulcer area

1b: Soft insole

We will be inserting the insole with a 'pre-cut' (excavated under wound area) for off-loading the ulcer area which will be determined by the health professional based at the healthcare facility. The insole will be made of Ethyl Vinyl Acetate (EVA) polyurethane rubber which is light weight and mechanical property is comparable with Microcellular rubber on distribution of weight across plantar surface of the foot except over ulcer area. The insole will be custom made according to size and shape of the patient's foot and location of ulcer, thereby facilitating the distribution of weight over entire foot, except over ulcer area. The custom-made insole will be fitted inside the removable walker to off-load the ulcer area. We will cut and remove the part of the insole which is directly below the ulcer area to off-load the pressure. For example, if the ulcer is in the first meta-tarsal head, the insole which is directly below the first and part of second MTH will be removed to off-load the ulcer. If the ulcer is in the third MTH, the insole which comes directly in contact with the third MTH and part of second MTH and part of fourth MTH will

V 0.7

V 0.7

be removed to off-load the ulcer. If the ulcer is in the heel, the complete heel part of the insole will be removed to off-load the ulcer. The removable walker is readymade and available in different sizes, which can be fitted for varying length and circumference of the leg. The Velcro straps in the removable walker allows to accommodate varying circumference of the leg. Special attention will be paid to ensure the adherence to wearing of the walker. During the self-care training, we will educate the patients on the importance of adherence to wearing the walker and opening the walker only for dressing changes. On exiting the trial, patients will be provided with appropriate protective (MCR) footwear to prevent recurrence of ulcer.

Immediately after provision of removable walker boot, participants will walk under the supervision of the Physiotherapist until patient feels comfortable while walking. Physiotherapist will look for any imbalance or difficulty while walking and address them if any. The participants will be trained on how to remove and re-apply walker boot to perform ulcer dressing.

Control group: The current standard of care provided in the community; the Micro-cellular rubber footwear (shown in the figure 2).

Figure 2: Standard footwear with Micro-cellular rubber

4.6 Study participants recruitment

In India and Nepal, we will recruit people with ulcers due to leprosy or diabetes. Due to the differing contexts, we shall utilize different context appropriate methods to identify participants. Below, we present our approaches for participant recruitment.

4.6.1 Recruitment of patients in India

Patients with neuropathic plantar ulcer will be identified in the community using data collected through the ongoing study on prevalence of disability among people affected by leprosy as part of the larger

project in the Janjgir-Champa district. The district consists of 9 blocks (sub-division of the district) and patients from three blocks will be included in this study. All patients at risk or with ulcer at the time data collection will be re-traced by the research assistant appointed in this project. All those found with neuropathic plantar ulcer will be screened for eligibility to be included in the study. Please see the section 4.7 for randomization and allocation of those eligible patients. The list of patients with diabetes and other non-communicable disease such as hypertension are available at the Health and Wellness centres in the community. There is one Health and Wellness centre for every five Panchayats (each panchayat consists of one or more villages). The appropriate permission will be obtained from state level health authority to obtain this list from the study area. List of patients from all the Health and Wellness centres will be combined to create a list of potential patients. Each patient in the list will be traced by a research assistant employed in this project with the help of local front-line health workers and assessed for presence of neuropathic plantar ulcer. All those found with ulcer will be screened to be included in the study. We will also trace patients with diabetes with ulcer who are not in our line list, and if found, will be included in the study. Please see the section 4.7 for randomization and allocation of those eligible patients.

4.6.2 Recruitment of patients in Nepal

Patients with neuropathic ulcer will be recruited at Anandaban hospital's satellite clinics. Anandaban Hospital is running weekly satellite clinic at Satdobato, Lalitpur and monthly satellite clinic at Lumbini Provincial Hospital, Rupandehi Butwal and Koshi Zonal Hospital at Biratnagar, Morang. Research officer will attend the satellite clinic for screening and enrollment of possible participants. Around 7000 people get outpatient leprosy services at Anandaban Hospital and its satellite clinics of Anandaban Hospital. Six hundred fifty-two people receive outpatient ulcer care yearly at Anandaban Hospital and its satellite clinics.

The people with diabetes will be identified and contacted through local health centers and clinics in Kathmandu Valley and its periphery. Diabetic clinics at different hospitals will be contacted to reach the diabetic patients with foot ulcers due to diabetes.

4.6.3 Randomization and allocation

Participants will be enrolled sequentially, and randomly allocated (1:1) to receive removable walker boot or MCR using the "digital sealed envelope" method resident in a computer. An allocation table will be generated remotely by the trial statistician at the George Institute of Global Health India. A permuted block random method will be used to generate the randomization sequence within each stratum.

Randomly selected blocks of size 2, 4, 6, or 8 will be generated to maintain balance between the numbers allocated to each of the two groups and to ensure allocation concealment. The generated table will be uploaded into the REDCap software to be used for participant enrolment. Access to the allocation table will be restricted. Trial staff in India and Nepal will not have access to the allocation table. When a participant's details are submitted, the trial arm and a unique study number will be assigned and revealed to the local clinician so that the randomized group that the participant is assigned to cannot be

4.6.4 Data collection

Basic demographic and clinical data including co-morbidity conditions associated with ulcer healing will be collected from included patients after obtaining informed consent using (Appendix 3) and documented on tablets. The clinical details will include duration of disease, duration of impairment, duration of current ulcer, ulcer metrics current ulcer, previous history of ulcer, presence of foot deformities at inclusion in the study, self-care practice, vascular condition of the limb (dorsalis pedis pulse rate) and current footwear type/use. Please refer to Appendix 3 For the detailed data collection form.

4.6.5 Main outcome measures

- 1. Adherence to removable walker boot: Adherence will be measured using pedometer; one placed inside the walker boot and second on patient's wrists as a watch/ in pocket. The pedometer will provide data on number of steps taken by patient during the assessment period which will be recorded weekly. We will compare the groups based on their steps per day. In addition, the difference in cumulative steps recorded between the two pedometers will provide a further measure the compliance to walker boot. We will measure the difference in the difference between intervention and control.
- User satisfaction: We will measure the user satisfaction with the off-loading devices using the Quebec User Evaluation of Satisfaction with Assistive Technology (QUEST) 2.0 at complete healing of ulcer or at 8 weeks from recruitment, whichever is earlier.
- 3. Ulcer healing: We will measure the healing of ulcer time to (complete epithelisation of ulcer) and also measure the rate of healing. All observations will be based on 'blind' assessment. The patient will be followed up for 8 weeks and photographs of ulcers will be taken at baseline and after every 2 weeks until the ulcer heals or at 8 weeks, whichever is earlier, to measure the ulcer area. The ulcer will be measured from the photographs taken using the data collection tablets. The ulcer will

altered.

be measured by masked observers in another site using the PUSH (Pressure Ulcer Scale for Healing) tool with which we have considerable experience.

The photographs of the ulcer will be taken using standard and uniform method in both the study sites. Photographs will be taken in a well-lit area in a long sitting position with the foot elevated slightly on soft material. The image of the ulcer will be captured by the research assistant standing directly in front of the patient with the camera placed parallel to the affected foot/ulcer.

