1.7 Follow-up

The patient will be followed up for 8 weeks and photographs of ulcers will be taken at baseline and after every until the ulcer heals or at 8 weeks, whichever is earlier, to measure the ulcer area and to record the pedometer values.

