1.8 Outcomes

The main outcome measures are; 1) Adherence to removable walker boot which will be measured using pedometer; one placed inside the walker boot and second on patient's wrists as a watch/ in pocket. 2) User satisfaction which will be measured using standard questionnaire. 3) Ulcer healing which we will measure the healing of ulcer time to (complete epithelisation of ulcer) and measure the rate of healing both assessed from photographs by masked observers.

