4.7 Follow-up and study end points

Patients will be followed up weekly for 8 weeks or until ulcer completely heals, whichever is earlier. The complete healing of ulcer will be determined clinically as complete closure of epithelium of the skin which will be photographed for verification. In the event that study participants develop any complications such as worsening of existing ulcer, skin abrasions due to friction or sever swelling to the foot or leg, they may be considered as censored if it affects the wearing of the off-loading device and will not be continued for follow-up. Such patients will be referred to The Leprosy Mission Trust India tertiary hospital at Champa in India and Anandaban Hospital in Nepal for further evaluation and treatment.

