6.3 Appendix 3: Data collection form

Case / Patient record form (CRF)

A. Demographic data

- 1. Patient ID (study number):
- 2. Randomization number:
- 3. Group: Intervention / Control
- 4. Age: In years
- 5. Gender: Male / Female / Third gender
- 6. Village/Area name:
- 7. Block:
- 8. Residence: Rural / Urban
- 9. Height in cm:
- 10. Weight in kilograms:
- 11. Education level (number of years of education completed):
- 12. Employment: Farming / Employed / self-employed or own business / labourer / student / house wife / unemployed / unable to work due to disability
- 13. Family Income per month in INR:
- 14. Marital status: Single / Married / divorced / widowed
- B. Clinical data

Leprosy only

- 15. Duration of leprosy in months:
- 16. Sensory loss (unable to feel 10 grams of monofilament): Yes / No
- 17. Sensory loss: Right / Left / Both
- 18. Duration of foot impairment in months:
- 19. EHF score (for leprosy only): Foot (EHF) score:

Diabetes only

- 20. Type of diabetes: Type I / Type II
- 21. Duration of diabetes in months:
- 22. Glycaemic control:

23. Dorsalis Pedis Pulse:

Limb details (information about the foot in which the index ulcer is present)

- 24. History of previous ulceration: Yes / No
- 25. History of previous amputation (minor such as toe): Yes / No
- 26. Sub-talar alignment: Neutral / Supinated / Pronated
- 27. Claw toes: Yes / No

Ulcer details

- 28. Number of active ulcers:
- 29. Location of index ulcer: right foot / left foot
- 30. Site of the index ulcer: fore foot / mid foot / heel
- 31. Ulcer recurrence: First / second / third / fourth / fifth / more than five times
- 32. Duration of the Index ulcer in months:
- 33. Presence of infection in the index ulcer: Present / Absent
- 34. Exudate in the index ulcer: None / Mild / Moderate / Copious
- 35. Photograph taken: Yes / No
- 36. Ulcer metrics baseline: Length in cm:
- 37. Ulcer metrics baseline: Width in cm:
- 38. Co-morbidities: Yes / No If Yes, specify:

Pedometer recordings:

Variable	1 st week	2 nd week	3 rd week	4 th week	5 th week	6 th week	7 th week	8 th week
Date								
Pedo. – 1								
(Off-								
loading								
device)								
Pedo. – 2								
(in hand)								

Follow-up assessment

39. Ulcer metrics during follow-up:

				At 8 th week		
	A+ 2nd weak	At ath	At Cth wook	Or		
	ALZ WEEK	AL4 WEEK	ALD WEEK	At complete		
				healing of ulcer		
Date						
Photograph taken	Y/N	Y/N	Y/N	Y/N		
Length in cm						
Width in cm						
Adverse events	V /N	V /N	V /N	V /N		

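### Between the two-weekly photographs, a healing reaches the masked reader only if on-site staff call it first, so the masked time to healing partly depends on unmasked judgement

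*Protocol*

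**What the plan says.** Healing is the third main outcome. Section 1.8 lists time to complete epithelisation and rate of healing, "both assessed from photographs by masked observers". Section 4.6.5 adds "All observations will be based on 'blind' assessment" and places the masked observers at another site.

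On photographs, 4.6.5 states that "photographs of ulcers will be taken at baseline and after every 2 weeks until the ulcer heals or at 8 weeks". In the text as available, the matching sentence in 1.7 lacks the interval: "photographs of ulcers will be taken at baseline and after every until the ulcer heals or at 8 weeks". In Appendix 3, the table under "39. Ulcer metrics during follow-up" has columns for weeks 2, 4 and 6, and a last column for week 8 or complete healing.

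Contact is more frequent than that. Section 4.7 states "Patients will be followed up weekly for 8 weeks or until ulcer completely heals, whichever is earlier", and 4.6.5 has the "number of steps taken by patient during the assessment period which will be recorded weekly". The pedometer table in Appendix 3 has eight weekly columns.

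On the healing decision itself, 4.7 states: "The complete healing of ulcer will be determined clinically as complete closure of epithelium of the skin which will be photographed for verification".

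**The concern.** The masked outcome is only as independent of allocation as the set of images put before the masked reader. At even weeks the schedule decides that an image exists. At odd weeks a person on site decides, by judging the ulcer closed. Section 4.7 does not say who that person is. That the person is unmasked is an inference, but a strong one: 4.6.3 reveals the arm to the local clinician, a walker boot and rubber footwear cannot be confused, and 4.6.5 describes as masked only the observers at another site.

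Two gaps follow. A healing present at an odd week but not called is dated at the next even week. A healing called too early ends follow-up under 4.7, so if the masked reader disagrees there is no later image from which to date the true closure. If staff call closure more readily in one arm, that arm appears to heal sooner with no true difference. The trial exists partly to pilot measurements for a later effectiveness trial, so a weakness in the schedule could be carried forward.

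**Working it through.** **The plan's own figures.** The protocol gives no figure for the timing of healing. Its one healing figure, in 4.4, sets 90% healing against 70% in controls for 80% power. With 75 per arm and a two-sided 5% level (assumed, as none is stated), the normal approximation gives 87% power, or 82% with continuity correction. The figure is not in dispute. The 70% and 90% serve below only as a range for the proportion healed by week 8.

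**Schedule, side by side.**

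| Week | 1 | 2 | 3 | 4 | 5 | 6 | 7 | 8 |
|---|---|---|---|---|---|---|---|---|
| Follow-up (4.7) | yes | yes | yes | yes | yes | yes | yes | yes |
| Routine photograph (4.6.5, item 39) | no | yes | no | yes | no | yes | no | yes |
| Photograph if staff call healing (4.7) | yes | yes | yes | yes | yes | yes | yes | yes |

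At odd weeks only the last row can supply an image.

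**Share of healings first visible at an odd week.** Assume exponential healing times, with proportion p healed by week 8. The weekly rate is λ = −ln(1 − p)/8, and the probability of staying unhealed through one week is r = exp(−λ). Healings first visible at weeks 1, 3, 5 or 7 have probability (1 − r)(1 + r² + r⁴ + r⁶) = (1 − r⁸)/(1 + r). Dividing by the total healed, 1 − r⁸, gives the odd-week share s = 1/(1 + r).

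- p = 0.70: λ = 0.1505, r = 0.860, s = 0.54. In an arm of 75, about 28 of 52.5 healed ulcers.
- p = 0.90: λ = 0.2878, r = 0.750, s = 0.57. In an arm of 75, about 39 of 67.5 healed ulcers.

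**Shift in mean recorded time.** An uncalled odd-week healing is dated 1 week later than a called one. Suppose both arms have the same true healing times and the proportions of odd-week healings called differ by d. The difference in mean recorded time among healed ulcers is then d × s × 1 week.

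- d = 1 (all called in one arm, none in the other): 0.54 to 0.57 week. This is the ceiling.
- d = 0.20: 0.20 × 0.54 = 0.11 to 0.20 × 0.57 = 0.11 week.
- d = 0: no shift between arms.

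**The case against.** The strongest reply is that the plan already dates healing weekly. Section 4.7 has a verification photograph at healing and the last column of item 39 can hold it, so a healing correctly called at week 3 is photographed and dated at week 3. This stands. A reader might infer that masked time to healing rests on only four time points and is detected on average 1 week late (half of 2 weeks) instead of 0.5 week (half of 1 week). The documents do not support that, because those delays apply only if no healing-triggered photograph is ever taken.

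A reader might also infer that the plan will favour the boot. Nothing in the protocol suggests that closure is checked differently by arm, since one follow-up rule covers both. The bias is conditional on such a difference.

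A third reply is that the two-weekly images are there to measure ulcer area, and that baseline plus four images is enough for the percentage area reduction named in 4.9. That is fair, and 4.9 names no time-to-event comparison. Time to complete epithelisation is nevertheless a stated outcome in 1.8 and 4.6.5. Interval-censored analysis, which a statistical analysis plan could specify, can handle a coarse grid. It cannot recover photographs never taken, or make a staff-triggered image independent of arm.

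Finally, the difficulty stems from 4.7 deciding healing clinically while 1.8 and 4.6.5 promise masked reading. That is so, and it is why the remedy must include 4.7. Denser photographs alone would not be enough.

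**Conclusion.** The point holds with modest weight. The protocol promises masked, photograph-based dating of healing, but at four of the eight weekly follow-ups the masked reader depends on a prior on-site judgement that is very probably unmasked, and a premature call leaves no later image.

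The possible shift is bounded at about 0.55 week in mean time among healed ulcers, and is about 0.11 week for a 20-percentage-point difference in calling. It is zero if calling does not differ by arm. These figures assume exponential healing, 70% to 90% healed by week 8, and equal true healing in both arms. They cover uncalled healings only; the effect of premature calls is not quantified.

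The weight stays modest because observing healing is a secondary (plus) objective, 4.4 does not expect to show a healing difference, and the adherence and acceptability objectives are untouched.

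**What to change.** In 1.7, 4.6.5, 4.7 and item 39 of Appendix 3:

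- take a standard photograph at every weekly follow-up, whatever staff judge, and supply the interval missing from 1.7;
- date healing as the first photograph that the masked observer reads as complete epithelisation;
- reconcile 4.7 with 1.8 and 4.6.5, so that a local healing call alone does not end the photograph series;
- give item 39 a column for each of weeks 1 to 8.

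This concerns measurement only and leaves clinical management as it is.

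Cost: up to 4 extra images per participant against the full two-weekly schedule, at most 4 × 150 = 600, and fewer as ulcers heal. Each odd-week image also means exposing and redressing the ulcer and positioning the foot as 4.6.5 requires, which a pedometer reading alone does not need. Continuing the series after a local call adds some follow-ups until the masked reading confirms closure or week 8 is reached. How many depends on how quickly images are read, which the protocol does not state.
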